layer of Crisaborole (2% BID) or vehicle twice daily (excluding mouth, eyes, and vagina, per label), to all locations with active lesions and record location and time of application on the daily dosing form (as identified on the Dosing Record Sheet, breastfeeding women will be instructed to use the provided gloves when applying crisaborole/vehicle). The study will be comprised of an initial screening/baseline visit for children participants who have an existing diagnosis of symptomatic AD, screened and enrolled in the study along with their primary caregivers after signing an informed consent (or parents/guardians and assent when appropriate). Upon enrollment child participants and caregiver participants will complete a one week acclimation and training phase, where the children will not be on medication, for wearing accelerometry/actigraphy and performing observer-reported outcome assessments (caregivers for participants) and self-reported outcome assessments (caregivers). After the one week acclimation and training phase, the child participants will be on a Crisaborole or vehicle treatment for two consecutive weeks. During those 2 weeks, the children, 3 months up to <2 years will wear one actigraphy or one accelerometry device on each wrist and one actigraphy or one accelerometry device on each ankle (optional for those who have active AD on location of device placement, with a minimum of at least one wrist device needed for enrollment). Children 2 years to \leq 11 years will wear one actigraphy or one accelerometry on each wrist (optional for those who have active AD on location of device placement, with a minimum of at least one wrist device needed for enrollment). The primary caregiver (parents/guardians) will also wear one accelerometer device on each wrist and complete daily assessments related to scratching, sleeping habits, pain, AD severity, quality of life, and device comfort questionnaires (parent/guardian will complete as appropriate). The participants will be asked to return to the laboratory on days 1, 2, 8, and 15 for assessments and biomarker assessment. At the completion of the study, Day 15 (\pm 3 day) participants (and primary caregiver) will return the devices, and will complete additional questionnaires. Participants may come in for an unscheduled visit as needed (i.e., to replace compound, etc.). During the performance of the study, participants will be monitored by the study dermatologist, and assess participant continuation throughout the study.

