Observer Reported Itch Assessment (ORIA; 3 months - ≤ 11 years old)		X	-----DAILY (Day 1-15 AH)----			X
Patient Reported Itch Severity Scale (6 years - ≤ 11 years old)		X	-----DAILY (Day 1-15 AH)----			X
Observer Global Impression of Severity (OGIS)		X	-----DAILY (Day 1-15 AH)----			X
PPNRS Caregivers		X	-----DAILY (Day 1-15 AH)----			X
Sleep:CSHQ (Age ≥4 - ≤ 11 years)/BISQ(Age 3 months - <4 years)/MOS-Sleep (Caregivers)		X	X		X	X
Observer Global Impression of Change (OGIC)					X	X
Device Comfort Questionnaire (DCQ)/Observer Device Comfort Questionnaire (ODCQ)						X
Mobile Device Proficiency Questionnaire (MDPQ)		X				
Faces, Legs, Activity, Cry, and Consolability Scale (FLACC)		X	X		X	X
Dermatitis Family Impact Questionnaire (DFI)		X	X		X	X
Children's Dermatology Life Quality Index (CDLQI) (Age ≥4 to ≤ 11 years) OR Infants Dermatitis Quality of Life Index (IDQOL) (Age 3 months to <4 years)		X	X		X	X
Patient-Oriented Eczema Scale (POEM) (observer-reported for participants age 3 months-11 years)		X	X		X	X
SAFETY						
Serious and non-serious AE monitoring	X	X	-----			X
STUDY INTERVENTION						
In-laboratory dose application training			X		X	
At home dosing and dosing record sheet (twice daily)					-----DAILY-----	
Drug dispensing			X			
DIGITAL HEALTH TECHNOLOGIES °						
Issue/Train/Retrieve Accelerometry Device; (Children: Ages 2 years to ≤ 11 years; On R & L wrists); (Caregivers: Ages 18 to 75 years; On R & L wrists)****		X Issue			X Retrieve, Re-Issue	X Retrieve
Accelerometry Wear (Children: Ages 2 years to ≤ 11 years; On R & L wrists); Caregivers: Ages 18 to 75 years; On R & L wrists) ****		X	-----			X
Issue/Train/Retrieve actigraphy or accelerometry (Ages 3 months up to <2 years; On R & L wrists and R & L ankles); (Ages 2 years to ≤ 11 years; On R & L wrists) ****		X Issue				X Retrieve
Actigraphy or accelerometry Wear/Measures Collected (Ages 3 months up to <2 years; On R & L wrists and R & L ankles); (Ages 2 years to ≤ 11 years; On R & L wrists) ****		X	-----			X

Period/Visit	Screening	V01 (Baseline)	V02	V03	V04	V05
Day	-28 to -7	-7	1	2	8	15
Window(days)	NA	+/- 3	+/- 3	+ 0.5	+/- 3	+/- 3

*per AD = atopic dermatitis; AE= adverse event; BISQ= Brief Infant Sleep Questionnaire; CSHQ= Children's Sleep Health Questionnaire; L= Left; MOS= Medical Outcomes Study; R= Right; V=Visit number; AH = At Home
 ‡ Participants are randomly assigned to one of the two arms of the study

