5. STUDY PROCEDURES

The study will consist of a screening/baseline (in- laboratory) visit on Day -7 (V01), an in- laboratory visit Day 1 (V02), an in- laboratory visit on Day 2 (V03) for tape-stripping, and Day 8 (V04) for an assessment of the severity of the AD and a final in- laboratory visit on Day 15 (V05) for an assessment of the AD, tape-stripping, completion of ObsROs and return devices. Throughout the study, the participants and caregivers will wear accelerometry/actigraphy devices continuously (optional for those who have active AD on location of device placement, with a minimum of at least one wrist device needed for enrollment; devices may be removed for short periods of time for such things as the purposes of bathing, etc.). Enrolled participants will be randomly assigned to each arm of the study. Participants may come in for an unscheduled visit as needed (i.e., to replace compound, etc.). All in-person study activities, including informed consent and pregnancy testing, will be completed at the Laboratory for Human Neurobiology, [name]. All activities performed in the laboratory are accomplished in private rooms. Primary caregivers will be provided with ample time and a privacy curtain to change into a gown during assessment for exclusion of Atopic Dermatitis, and primary caregivers will accompany children during all activities to ensure participant privacy. All at-home study activities will be completed in the participants' home.

Phone Screening - Day-28 to -7 (~15 minutes):

- Verbal consent (including assent where applicable)
- Assign Participant ID (a sequentially assigned numerical ID used to identify participant on all study documents and in the electronic data capture [EDC] system)
- Screening demographics, medical history including AD history/treatment (includes, race, ethnicity, and gender)
- Eligibility screening (review of inclusion and exclusion criteria)

Baseline Visit 1 (V01)/Day -7 (+/- 3) – In Laboratory (~2 hours):

- Written Informed consent (including assent when applicable)
- Participants are randomly assigned to one of the two arms of the study
- Screening demographics (includes race, ethnicity, gender, and significant medical

history/treatment)

- Pregnancy test for female caregivers of child-bearing potential
- Wide Range Achievement Test 4 (WRAT-4)
- Eligibility Screening (Inclusion/Exclusion criteria)
- Vital signs
- Height and weight

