- Investigator's Static Global Assessment (ISGA) (scored by a dermatologist or a medically qualified individual who has been trained in the assessment; rater to be consistent throughout study)
- EASI assessment (scored by a dermatologist or a medically qualified individual who has been trained in the assessment; rater to be consistent throughout study)
- Calculate % body surface area (BSA) affected with AD
- Childhood Asthma Control Test
- Tape Stripping (Biomarker Assessment)
- Observer Reported Itch Assessment (ORIA; ages 3 months - ≤ 11 years)
- Patient Reported Itch Severity Scale (ages 6 years to ≤ 11 years old)
- Observer Global Impression of Severity (OGIS; ages 3 months - ≤ 11 years)
- Peak Pruritis NRS (Caregivers)
- Children's Sleep Health Questionnaire (CSHQ; ages ≥4-≤ 11) OR Brief Infant Sleep Questionnaire(BISQ; ages 3 months-<4 years)
- Medical Outcome Sleep Scale (MOS; caregivers only)
- Mobile Device Proficiency Questionnaire (MDPQ; caregivers only)
- Faces, Legs, Activity, Cry, and Consolability Scale (FLACCS)
- Dermatitis Family Impact Questionnaire (DFI; parent/guardian(s); ages 3 months- ≤ 11 years)
- Children's Dermatology Life Quality Index (CDLQI; ages ≥4-≤ 11 years) OR Infants Dermatitis Quality Of Life Index (IDQOL; ages 3 months-<4 years)
- Observer-reported Patient-Oriented Eczema Measure (POEM); ages 3 months – ≤ 11 years)
- The participant will be asked to don the accelerometry/actigraphy devices (coordinator will log dispensing) as follows: The participant will be provided the accelerometry/actigraphy devices immediately after completion of informed consent and will be trained. Devices will be optional for child participants who have active AD on location of device placement, with a minimum of at least one wrist device needed for enrollment.
 - Accelerometry
 - Children: Ages 2 years to ≤ 11 years; On R & L wrists
 - Caregivers: Ages 18 to 75 years; On R & L wrists
 - Actigraphy or accelerometry:
 - (Ages 3 months up to ≤ 11 years; On R & L wrists and R & L ankles for 3 months - <2 years; R & L wrists only for 2 – ≤ 11 years)

Out-of-Laboratory (At-Home) Assessments (Days -7–Day 1; Between Visits 1 & 2):

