The purpose of the out-of-laboratory assessment is to evaluate wearable devices in a home/routine setting (defined as the participant's routine environment/activities). Participants will be provided a fully-charged set of accelerometry devices for use at home. Devices will be optional for child participants who have active AD on location of device placement, with a minimum of at least one wrist device needed for enrollment.

1. Continuously wear Accelerometry devices as much as possible

2. Continuously wear Actigraphy devices as much as possible

Visit 2 (V02)/ Day 1 (+/- 3 days)- In Laboratory (~1 hour):

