The primary and secondary endpoints will be tested at the significance level of 0.05 (2-sided). There is no multiplicity adjustment. Number, percent and 95% confidence interval (CI) will be presented for binary endpoints. Descriptive summary statistics (n, Mean, Std. Dev, Median, Min., Max.) will be presented for continuous endpoints. In addition, graphics may be used to present the data.

The primary objective is to evaluate the effects of Crisaborole on itch and night-time scratch. The primary endpoints include number of scratching episodes (children aged 2 – \leq 11 years), duration of scratching (children aged 2 – \leq 11 years), and ORIA (ages 3 months to \leq 11 years). For these endpoints, change from baseline will be analyzed using a mixed-effects model with repeated measures (MMRM) including data from Day 1 (for accelerometry measured scratch episodes and duration)/Day 2 (for ORIA) to Day 15 with baseline score as a covariate and an unstructured covariance matrix. The least-squares (LS) means and

the corresponding 95% CIs, the LS mean difference between treatment groups, and the corresponding 95% CI will be presented for change from baseline for all postbaseline timepoints. As a sensitivity analysis, instead of daily data, average of every 3 days data will be used to account for day-to-day variation.

The binary endpoints will be descriptively summarized using sample size, number, percentage and 95% confidence interval (CI) of percentage at each time point. Binary data will be analyzed by comparing response rates between treatment groups. Normal approximation to the difference in response rates will be used to obtain p-values and 95% CI. For binary endpoints analyzed at each scheduled visit separately, participants who drop out for any reason or require a prohibited medication for the treatment of their atopic dermatitis will be defined as “non-responsive” at all subsequent visits. This method of handling missing response is known as missing response as non-response (MR-NR).

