Appendix B: PATIENT REPORTED OUTCOME (PRO) / OBSERVER REPORTED OUTCOME(ObsRO) ASSESSMENTS

Observer Reported Itch Assessment

The Observer Reported Itch Assessment assesses the severity of itch (pruritus) in the child due to AD. The participants primary caregiver will be asked to assess their child's worst itch (i.e., scratching, rubbing) due to AD over the past 24 hours in an eDiary every day during the study. Observer Reported Itch Assessment for 3 months - ≤ 11 years of age is an 11-point scale and must be completed by an observer (caregiver). Instruments to be provided to participants as age appropriate below:

Subject ID: _____

Date: _____

Observer Reported Itch Assessment for ages ≥3 months to <2 years of age:

On a scale of 0 to 10, with 0 being "no itch" and 10 being "worst itch imaginable", how would you rate your observation of your child's itch (i.e., scratching, rubbing) at the worst moment during the previous 24 hours?

Cannot answer. I am unable to observe signs of itch-related

|

Subject ID: _____

Date: _____

Observer Reported Itch Assessment for ages ≥ 2 years to ≤ 11 of age:

On a scale of 0 to 10, with 0 being "no itch" and 10 being "worst itch imaginable", how would you rate your observation of your child's itch (i.e., scratching, rubbing) at the worst moment during the previous 24 hours?

Subject ID: _____

Date: _____

Technician Initials: _____

PAD Patient Reported Itch Severity Scale for 6-11 years of age:

Select the face that shows how itchy your skin has been today:

Not Itchy

Very Itchy

Subject ID: _____

Date: _____

Observer Reported Global Impression Severity (OGIS)

The scale will be completed by an observer every day, preferably at the same time as the Observer Reported scratch assessment. The Observer Reported Global Impression Severity (OGIS) is a one-item 7-point rating scale and completed by observers/caregivers of subjects to assess a subject's illness severity at a given point in time. The OGIS will be used as an anchor for defining a "clinical important difference" on the scratch assessments and can also be used to create severity categorization to enhance interpretation. The observer/caregiver of a child is asked to rate the severity of an illness of the child right now as follows:

Please rate the severity of the child's atopic dermatitis right now (select only ONE response):

Not present	
Very mild	
Mild	

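### No baseline is defined for the three primary endpoints, and the schedule leaves ORIA with only single pre-dose ratings although an untreated week is available to average over

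*Combined protocol and SAP*

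**What the plan says.** Section 9 (Data Analysis) names three primary endpoints: number of scratching episodes, duration of scratching, and ORIA. Each is analysed as change from baseline in a repeated-measures model "with baseline score as a covariate and an unstructured covariance matrix". The post-baseline data run from "Day 1 (for accelerometry measured scratch episodes and duration)/Day 2 (for ORIA) to Day 15". No day, visit or averaging window is given for the baseline itself.

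Elsewhere the documents say:

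- **Visit label.** Section 5 and the Schedule of Activities attach the word baseline to one visit, "Baseline Visit 1 (V01)/Day -7 (+/- 3".
- **Devices.** Section 5 has them issued at V01, "immediately after completion of informed consent and will be trained". The home list for Day -7 to Day 1 then asks families to "Continuously wear Accelerometry devices as much as possible" and does the same for actigraphy. It lists nothing else.
- **ORIA in the schedule.** The row shows V01, then "DAILY (Day 1-15 AH", then V05.
- **ORIA in Appendix B.** The caregiver rates the worst itch of the past 24 hours "in an eDiary every day during the study".
- **Acclimation week.** The synopsis and Section 3 describe an unmedicated week "for wearing accelerometry/actigraphy and performing observer-reported outcome assessments".
- **Entry rule.** Section 4.1 requires an ORIA of at least 2 at Day -7 for ages 3 months to 5 years. Ages 6 to 11 qualify on the Patient Reported Itch Severity Scale instead.

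**The concern.** Every primary estimate depends on the baseline value, as the quantity subtracted and as the covariate. Taken literally, the visit label cannot serve two of the three endpoints, because no night has been recorded by V01. For ORIA, the schedule offers V01, taken about a week before dosing and in the younger children the value that admitted them, or Day 1. Each is a single rating of a symptom likely to vary from day to day.

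Three things are at stake:

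- A single rating is a weaker covariate than an average, so precision is lost.
- If the screened V01 rating is used, part of each arm's improvement is regression to the mean. This matters because Section 9 also plans comparisons of the start of the study with on-treatment values.
- Section 9 says that both the laboratory and the sponsor will run analyses. They could choose different baselines, with no text to settle which is primary.

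If the schedule is followed, the acclimation-week ORIA data are never collected and cannot be recovered later.

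**Working it through.** **1. The plan's own figure.** Section 9 gives a 1.0-point difference, an SD of change of 2.6, 122 per arm and two-sided 5%.

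Power = Φ(1.0 / (2.6·√(2/122)) − 1.96) = Φ(3.004 − 1.96) = 85.2% (84.9% by noncentral t). Solving for n at 85% power gives 122 per arm, or 244. With 270 recruited and 10% lost, 270 × 0.9 = 243. The plan's figures reproduce. They use the SD of change with no gain from the covariate.

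**2. Pre-dose data available under each reading.**

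| Endpoint | At V01 | V01 to Day 1 | Day 1 |
|---|---|---|---|
| Scratch number and duration | none | nights recorded; no rule for using them | first post-baseline day in the model |
| ORIA, schedule and Section 5 | one rating | none | one home rating, outside the Day 2–15 model data |
| ORIA, Appendix B | one rating | daily | one rating |

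The Visit 2 clinic list does not include ORIA, so the Day 1 rating is a home entry. Its timing relative to the first application is not stated.

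**3. Length of the run-in.** V01 is Day -7 ± 3 and V02 is Day 1 ± 3. On the day numbers as printed, the gap is 8 ± 6, or about 2 to 14 days (one fewer at each end if there is no Day 0). A fixed 7-day window will not always be filled.

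**4. What averaging would gain for ORIA.** The day-to-day correlation ρ is not in the documents. I assume 0.3 to 0.8, equal between all pairs of days, and one post-baseline day as outcome. To keep the single-day SD of change at 2.6, the daily variance is s² = 2.6² / (2(1 − ρ)). With a k-day mean as covariate, the residual variance is s²·(1 − kρ² / (1 + (k − 1)ρ)).

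Example at ρ = 0.5: s² = 6.76. For k = 1, 6.76 × 0.75 = 5.07, SD 2.25. For k = 7, 6.76 × (1 − 1.75/4) = 3.80, SD 1.95.

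| ρ | 1 day: SD, power | 3 days: SD, power | 7 days: SD, power | Gain, 7 days vs 1 |
|---|---|---|---|---|
| 0.3 | 2.10, 96.1% | 2.00, 97.4% | 1.93, 98.1% | 2.0 points |
| 0.5 | 2.25, 93.4% | 2.06, 96.7% | 1.95, 98.0% | 4.6 points |
| 0.8 | 2.47, 88.6% | 2.10, 96.0% | 1.96, 97.8% | 9.2 points |

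The documents give no SD for scratch, so no such figure can be computed for it.

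**5. Does the entry cut bias the comparison?** A simulation applied the cut (ORIA of at least 2) to half the children, matching the target of about 50% aged 5 or younger. It assumed a mean ORIA of 4 or 6 and ρ of 0.4 or 0.6, with 2,000 trials per setting and the screened rating as baseline.

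- Treatment estimate: -0.99 to -1.00 for a true -1.0.
- Type I error: 4.0% to 5.5%.
- Vehicle-arm change caused by selection alone: 0.07 to 0.23 points of apparent improvement. With a 7-day mean that excludes the screened rating, it was within 0.01 of zero.

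**The case against.** The case for leaving this alone has several sound parts.

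- **Scratch.** A reader might infer that the scratch baseline is missing. It is not: devices are worn through the untreated week, so the nights exist and an analyst could use them. What is absent is the rule. One might also argue that the first nights of an acclimation week are unrepresentative; that is a choice to prespecify.
- **Day 1 ORIA.** The model starts scratch at Day 1 but ORIA at Day 2, which suggests that Day 1 was meant as the ORIA baseline. This is plausible and would weaken the complaint about a rating taken a week early. It is not stated, and Day 1 is still a single rating.
- **Selection.** A reader might take the V01 ORIA as entry-screened in everyone. The rule covers ages 3 months to 5 years only, and the cut is low on a 0–10 scale.
- **Acclimation week.** Section 3 does not name ORIA or daily collection. It is in tension with the schedule; the direct conflict is with Appendix B.
- **Power.** A reader might conclude that the trial is underpowered, or treat 2.6 as a residual SD that averaging would shrink. Section 9 gives it as the SD of change. On that basis, even a single-day covariate stays above 85% across the assumed range.

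What survives is that no text fixes the baseline, and that the schedule forgoes useful pre-dose ORIA data at odds with Appendix B.

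**Conclusion.** The point holds as a cheap improvement that should be made. It is not a threat to validity. Baseline is undefined for all three primary endpoints; V01 cannot supply it for scratch; and for ORIA the choice between V01, Day 1 and a run-in mean is open, with the documents disagreeing on whether run-in ratings will exist.

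For ORIA, a 7-day mean gains about 2 to 9 power points over a single day. This rests on 2.6 being the SD of change and on an assumed correlation of 0.3 to 0.8 that does not decay with time; fewer available days would gain less. Regression to the mean of 0.07 to 0.23 points would affect within-arm change only, and only if the screened rating is used. The documents do not support a claim that the treatment comparison is biased or that the stated 85% is wrong.

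**What to change.** - **Collection.** Start the daily ORIA eDiary at V01, and bring the schedule row and the Day -7 to Day 1 home list into line with Appendix B and Section 3. This helps only children enrolled after the change, so it is the urgent part.
- **ORIA baseline.** Use the mean of the available pre-dose daily scores in the last 7 days before first dose, including a Day 1 rating completed before the first application. State a minimum number of scores, with the last pre-dose score as fallback. Keep the V01 rating for eligibility and out of the mean.
- **Scratch baseline.** For number and duration, use the mean of valid nights from V01 to the night before first dose. Define a valid night, state a minimum number, and say whether the planned log(x+1) transformation is applied before or after averaging.
- **Timing.** Put these definitions in Section 9, binding on both analysis groups, before unblinding.

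The cost is a few sentences, one schedule row and one home-list entry, and about one extra week of a one-item caregiver diary.
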